6.3. Measures to Minimize Bias: Randomization and Blinding

Study Vaccine Allocation

Central randomization will be implemented in this study. On Day 1, participants will be randomly assigned in a 2:1 ratio to 1 of 2 groups (active vaccine or placebo) based on a computer-generated randomization algorithm prepared before the study by or under the supervision of the sponsor. Participants who have provided additional informed consent will be enrolled in the Safety Subset and/or in the Immuno Subset.

The interactive web response system (IWRS) will assign a unique code, which will dictate the group assignment and matching study vaccine kit for the participant. The requestors must use their own user identification and personal identification number when contacting the IWRS and will then give the relevant participant details to uniquely identify the participant.

To ensure balance across arms, the randomization will be stratified by age category (ie, 60-64 years, 65-74 years, 75-84 years, ≥ 85 years), and by being at increased risk of severe RSV disease (yes/no). Within strata, minimization will be applied for subset (being part of the Safety Subset only, the Immuno Subset only, both subsets or none), region (North America, Europe, SH), site, and stratum combination. The following caps will be installed for the global cohort:

- The total number of 60-64 year old participants will be a maximum of 2,000 participants. Depending on recruitment, caps might be installed with the aim to have ~10% 60-64 year old participants per region.
- The Safety Subset (including participants who are only in the Safety Subset and who are in both the Safety and Immuno Subset) will include at least 1,050 participants, ~50% of them will be at increased risk for severe RSV disease, ~50% of them will be 75 years or older.

The Safety Subset should contain ~750 participants from North America and ~300 from each of the other regions in the setting that these are part of the study. In each region,

~50% of the Safety Subset will be at increased risk of severe RSV disease and ~50% will be 75 years or older.

- The Immuno Subset (including participants who are only in the Immuno Subset and who are in both the Safety and Immuno Subset) will include at least 360 participants, ~50% of them will be at increased risk for severe RSV disease and ~50% will be 75 years or older.

The Immuno Subset should contain at least 180 participants from North America, at least 180 from Europe, and ~120 from each of the other regions in the setting that these are part of the study. In each region, ~50% of the Immuno Subset will be at increased risk of severe RSV disease and ~50% will be 75 years or older.

No other caps are installed for the Global cohort.

In each of the regions, the non-increased risk Safety Subset must be fully enrolled before further enrollment of non-increased risk participants. Also, the 60-74 years Safety Subset must be fully enrolled before further enrollment of participants aged 60-74 years. Similarly, in each region, the increased risk Safety Subset must be fully enrolled before further enrollment of increased risk participants. Also, the 75-years-and-older Safety Subset must be fully enrolled before further enrollment of participants aged 75 years and older. Immuno Subset participants will be enrolled only at a selection of sites.

Additional local cohort enrollment, beyond the Global cohort enrollment, may be allowed if required by local health authorities for the purpose of local regulatory approval consideration. This will also be handled via the IWRS and will follow the same randomization ratio as the Global cohort. Stratification and minimization will be done in a similar way as for the Global cohort. The number of 60-64 year old participants in those local cohorts will be a maximum 10% of the total cohort. Caps for the Immuno Subset and the Safety Subset will depend on local requirements.

Blinding

The investigator will not be provided with randomization codes. The codes will be maintained within the IWRS, which has the functionality to allow the investigator to break the blind for an individual participant.

In general, for the Global cohort, randomization codes will be disclosed fully only if the study is completed and the clinical database is closed. The participants, study site personnel (except for those with primary responsibility for study vaccine preparation and dispensing), and investigator will be blinded to the study vaccine allocation until the end of the study. The sponsor will be blinded to Day 1 study vaccine allocation until the database lock for the primary efficacy analysis except for the sponsor representatives involved in independent drug monitoring.

From the primary efficacy analysis onwards, group level results may be shared externally as needed, however, efforts will be made to preserve the blinding to the individual participant allocation until the end of the study.

For local cohorts, similar blinding principles hold. The randomization codes will be disclosed fully if the study of the local cohort is completed and the respective clinical database is closed, but not

before the global clinical database is closed. Local study teams will be blinded to study vaccination until the primary analysis as specified per local requirements, but this cannot be conducted prior to the primary analysis of the Global cohort.

For countries/territories that contribute to both the Global and the local cohorts, the randomization codes will be disclosed fully if the study of the local cohort is completed and the respective clinical database is closed, but not before the global clinical database is closed. The global study team of the sponsor will be unblinded. The local study teams will be blinded to study vaccination until the primary analysis as specified per local requirements, but this cannot be conducted prior to the primary analysis of the Global cohort.

The investigator may in an emergency determine the identity of the vaccination by contacting the IWRS. While the responsibility to break the vaccination code in emergency situations resides solely with the investigator, it is recommended that the investigator contact the sponsor or its designee if possible, to discuss the particular situation before breaking the blind. Telephone contact with the sponsor or its designee will be available 24 hours per day, 7 days per week. In the event the blind is broken, the sponsor must be informed as soon as possible. The date, time, and reason for the unblinding must be documented by the IWRS, in the appropriate section of the eCRF, and in the source document. The documentation received from the IWRS indicating the code break must be retained with the participant's source documents in a secure manner. The investigator is advised not to reveal the study vaccine assignment to the study site personnel or sponsor personnel/sponsor representative.

If the randomization code is broken by the sponsor for safety reporting purposes, the participant may remain in the study (if the randomization code is still blinded to the study site personnel and the participant).

Participants who withdraw will not be replaced.

6.4. Study Vaccination Compliance

Study vaccine (active or placebo) will be administered IM by a blinded vaccine administrator a trained and qualified study nurse, medical doctor, or otherwise qualified healthcare professional.

Details of study vaccine administration will be recorded in the eCRF (including date and time of injection and deltoid).

For details on blinding procedures, see Section 6.3, Measures to Minimize Bias: Randomization and Blinding.

6.5. Dose Modification

Not applicable.

6.6. Continued Access to Study Vaccine After the End of the Study

Participants will be instructed that study vaccine will not be made available to them after they have completed study vaccination.

6.7. Overdose

For this study, any dose of vaccine greater than the assigned dose will be considered an overdose. The sponsor does not recommend specific treatment for an overdose. In the event of a known overdose, the investigator should:

- Contact the medical monitor immediately.
- Closely monitor the participant for AE/SAE/AESI/medically-attended AE (MAAE) (ie, the participant will remain at the study site for at least 1 hour and will be closely monitored for allergic or other reactions by study staff. Follow-up telephone calls or telemedicine contacts 12 hours and 24 hours post-dose will be made).
- Document the quantity of the excess dose in the source document.
- Report as a special reporting situation.

6.8. Concomitant Therapy

For All Participants

Prestudy specific therapies such as analgesics/antipyretics and non-steroidal anti-inflammatory drugs (NSAIDs) administered up to 30 days before the dose of study vaccine must be recorded at screening. Use of analgesics/antipyretics and NSAIDs for routine prophylaxis prior to study vaccine administration is discouraged, however, should be used only in case of medical need and in line with local standard of care.

Concomitant therapies associated with SAEs, AESIs, and with AEs leading to discontinuation from study will be collected and recorded in the eCRF from the time of vaccination through the end of the study. Concomitant medications associated with RSV, hMPV, and influenza-mediated ARI episodes and with complications of RSV, hMPV, and influenza-mediated ARIs will be captured in the eCRF for the duration of the study.

The use of systemic corticosteroids must be documented throughout the study. Antineoplastic and immunomodulating agents, eg, cancer chemotherapeutic agents or chronic or recurrent use of systemic corticosteroids, or radiotherapy are prohibited throughout the study. If the use of systemic corticosteroids, antineoplastic or immunomodulating agents becomes medically indicated during the study for any participant, the sponsor should be contacted.

Vaccination with licensed live-attenuated vaccines within 28 days of the study vaccination (ie, before or after) is prohibited. Other licensed (not live) vaccines (eg, tetanus, hepatitis A or B, rabies) should be given at least 14 days before (or at least 14 days after) administration of study vaccine. If a vaccine is indicated in a post-exposure setting (eg, rabies or tetanus), it must take priority over the study vaccine.

For SARS-CoV-2 vaccines either licensed or available under Emergency Use Authorization: live-attenuated vaccines should be given at least 28 days before or after study vaccination; non-live vaccines should be given at least 14 days before or after study vaccination. A viral-vectored SARS-CoV-2 vaccine is not to be given within 28 days before or after study vaccination. Any history of

SARS-COV-2 vaccination (name/manufacturer of the vaccine and date of administration, whenever possible) prior to and during the study will be collected in the eCRF.

Seasonal influenza vaccination is recommended, but must occur at least 14 days before or at least 14 days after the study vaccine administration. Any history of influenza vaccination (name/manufacturer of the vaccine and date of administration, whenever possible) within 3 months prior to enrolment in the study to and during the study will be collected in the eCRF.

The sponsor must be notified in advance (or as soon as possible thereafter) of any instances in which prohibited therapies are administered.

For Participants in the Safety Subset

For participants in the Safety Subset, concomitant therapies associated with unsolicited AEs will be collected and recorded in the eCRF from the time of the study vaccine administration through 28 days after vaccination. Concomitant therapies associated with solicited AEs will be collected by the participants and recorded in the eCRF from the time of vaccine administration through 7 days after vaccination.

Information on concomitant use of herbal supplements or vitamins will not be collected.

7. DISCONTINUATION OF STUDY VACCINATION AND PARTICIPANT DISCONTINUATION/WITHDRAWAL

7.1. Discontinuation of Study Vaccination

Not applicable.

7.2. Participant Discontinuation/Withdrawal From the Study

A participant will be withdrawn from the study for any of the following reasons:

- Lost to follow-up
- Withdrawal of consent
- Death
- Repeated failure to comply with protocol requirements
- Any AE that requires discontinuation from the study
- Decision by the sponsor or the investigator to stop or cancel the study
- Decision by local regulatory authorities and Institutional Review Board (IRB)/ Independent Ethics Committee (IEC) to stop or cancel the study
- If the randomization code is broken by the investigator or the study site personnel.
Note: If the randomization code is broken by the sponsor for safety reporting purposes, the participant may remain in the study (if the randomization code is still blinded to the study site personnel and the participant).

When a participant withdraws before study completion, the reason for withdrawal is to be documented in the eCRF and in the source document. All efforts should be made for the participant to return the eDevice provided by the site, as applicable. If the reason for withdrawal from the study is withdrawal of consent then no additional assessments are allowed.

Withdrawal of Consent

A participant declining to return for scheduled visits does not necessarily constitute withdrawal of consent. Alternate follow-up mechanisms that the participant agreed to when signing the consent form apply as local regulations permit.

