The study is successful if:

- The lower limit (LL) of the 95% 2-sided confidence interval (CI, potentially corrected as described in Section 9.4.1.3) around the VE (1-relative risk rate) calculated from the Exact Poisson regression model is above 20% and additionally a point-estimate of VE $> 50\%$ is observed for Group 1

OVERALL DESIGN

This is a multicenter, randomized, double-blind, placebo-controlled Phase 3 confirmatory efficacy study in participants aged 60 years and older. The primary objective of the study is to further establish the efficacy of the active Ad26.RSV.preF-based study vaccine in the prevention of RT-PCR-confirmed RSV-mediated LRTD.

Up to approximately 27,200 participants (with up to approximately 23,000 in the Global cohort, and up to approximately 4,200 participants in specific Asian countries/territories under local protocols) will be enrolled and randomized in parallel in a 2:1 ratio to receive active study vaccine or placebo.

Note that some additional local cohort enrollment beyond the Global cohort enrollment may be allowed if required by local health authorities for the purpose of local health authority consideration.

- The Global cohort is defined as all participants (including the Safety subset and the Immuno subset) who are recruited up to the point that global enrollment is stopped.

- Local cohorts are defined as participants from the considered country/territory and under local protocols.

For analyses purposes, data from the Global cohort and the local cohorts may be aggregated. Analyses for local cohort enrollment will be described separately, but they will also be included in the primary analysis and final analysis if their enrollment started prior to the database cut-off of the primary analysis or final analysis, respectively.

The study includes 1 dose of study vaccine at Day 1.

The study will be discontinued if the primary analysis is performed by the sponsor and the outcome is negative; however, if at that timepoint, some participants have not completed 6 months of follow-up after their vaccination, the study will continue until this follow-up period is complete.

Study Design: VAC18193RSV3001

Group	N	Day 1
1	15,340	Ad26/protein preF RSV vaccine (1×10^{11} vp/150 µg)
2	7,670	Placebo

N number of participants, vp viral particles

ARI ASSESSMENTS AND PROCEDURES

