The blood samples that are collected between 2 and 4 days after symptom onset (ARI Day 3-5) from participants with an RSV, hMPV, or influenza-mediated ARI episode will be assayed by serology (which may include pre-F/post-F enzyme-linked immunosorbent assay (ELISA) and RSV virus neutralizing antibodies [VNA], as available and applicable) to assess immune responses and correlates that are associated with RSV infection. The samples will also be used for exploration of biomarkers that correlate with RSV infection and RSV disease severity (which may include RT-PCR for RSV, ribonucleic acid [RNA] transcriptomics to assess gene regulation [clusters] and expression patterns, cytokine/chemokine-dependent immunophenotyping, and immune repertoire analysis, as available and applicable).

SAFETY EVALUATIONS

For All Participants

All (S)AEs and special reporting situations related to study procedures or to non-investigational (concomitant) Janssen products will be collected from informed consent form (ICF) signature onwards until the end of the study for all participants. All other SAEs and AESIs will be collected from administration of study vaccine (Day 1) until 6 months after vaccination. AEs leading to discontinuation from the study will be collected for the duration of the study. All COVID-19 cases will be collected for all participants for the duration of the study.

ARIs and complications related to RSV, hMPV, and influenza-mediated ARIs that classify as SAE will be captured in all participants and reported as SAEs in the eCRF continuously from the time of vaccination until 24 months after vaccination.

All participants will be closely observed for a minimum of 15 minutes after vaccination to monitor for the development of any acute reactogenicity. This post-vaccination observation period should be extended for participants whom in the investigator's opinion would require further observation or for any occurrence of a localized reaction or (minor) systemic symptoms during the post-vaccination observation that require monitoring for any progression.

Vital signs will be collected prior to vaccination for all participants. At non-vaccination visits, vital signs will be measured if deemed necessary by the investigator.

For Participants in the Safety Subset

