8.4. Safety Assessments

For All Participants

All (S)AEs and special reporting situations related to study procedures or to non-investigational (concomitant) Janssen products will be collected from ICF signature onwards until the end of the

study for all participants. All other SAEs and AESIs (see Section 8.5.6) will be collected from administration of study vaccine (Day 1) until 6 months after vaccination. AEs leading to discontinuation from the study will be collected for the duration of the study. All COVID-19 cases will be collected for all participants for the duration of the study.

ARIs and complications related to RSV, hMPV, and influenza-mediated ARIs that classify as SAEs will be captured in all participants and reported as SAEs in the eCRF continuously from the time of vaccination until 24 months after vaccination.

All participants will be closely observed for a minimum of 15 minutes after vaccination to monitor for the development of any acute reactogenicity. This post-vaccination observation period should be extended for participants whom in the investigator's opinion would require further observation or for any occurrence of a localized reaction or (minor) systemic symptoms during the post-vaccination observation that require monitoring for any progression.

For Participants in the Safety Subset

Additional procedures will be carried out in the Safety Subset participants; ~50% of the participants in the Safety Subset will be at increased risk of severe RSV disease and ~50% will be 75 years or older (Section 6.3, Measures to Minimize Bias: Randomization and Blinding). Safety Subset participants will have provided consent for the additional study procedures^a:

- At the end of the 15-minute observation period, vital signs (body temperature, blood pressure, heart rate, respiratory rate, oxygen saturation) will be obtained^b, and any unsolicited and solicited local and systemic AEs will be documented in the eCRF by study personnel.

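### An investigator or site code break, including an emergency one, ends study participation, so scheduled collection of new SAEs/AESIs to Month 6 and ARI surveillance stop although the only dose has already been given

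*Protocol*

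**What the plan says.** Protocol Section 7.2 opens its list with "A participant will be withdrawn from the study for any of the following reasons", and one item reads "If the randomization code is broken by the investigator or the study site personnel". The only carve-out is for the sponsor: "If the randomization code is broken by the sponsor for safety reporting purposes, the participant may remain in the study", provided that the site and the participant stay blinded. Emergencies are not exempted.

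Protocol Section 6.3 (Blinding) gives emergency unblinding to the investigator: "The investigator may in an emergency determine the identity of the vaccination by contacting the IWRS". The same section places responsibility for that decision on the investigator alone.

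The Synopsis says "The study includes 1 dose of study vaccine at Day 1", and Section 7.1 (discontinuation of vaccination) is marked not applicable.

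On safety collection, Section 8.4 says "All other SAEs and AESIs (see Section 8.5.6) will be collected from administration of study vaccine (Day 1) until 6 months after vaccination". ARI surveillance runs to Month 24 (Section 8.1).

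On what may be done after withdrawal, Section 7.2 has one prohibition, limited to a different reason: "If the reason for withdrawal from the study is withdrawal of consent then no additional assessments are allowed". It sets no contact schedule for participants withdrawn for other reasons.

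**The concern.** In a multi-dose trial, withdrawing an unblinded participant can at least stop further dosing. Here no dosing remains, so the rule only ends observation. Emergency code breaks are not a random sample of participants: the reason for the break is likely to be an adverse event, so planned follow-up stops in a group selected for safety problems. At stake are new SAEs and AESIs in these people up to Month 6, and their later ARI episodes. The AESI work-up also leans partly on continued participation. Section 8.5.6.1 draws on Day 1 and Day 15 serum (Table 4) and on samples from an unscheduled or the next scheduled visit (Table 5). A participant withdrawn before Day 15 has neither a Day 15 draw nor a next scheduled visit.

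**Working it through.** No figure in the plan rests on this rule, so there is nothing to reproduce. The check sets the sections side by side and then sizes the effect.

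**1. Does emergency unblinding trigger withdrawal?** Section 6.3: the investigator breaks the code in an emergency. Section 7.2: a code break by the investigator or site means withdrawal from the study. Together: yes.

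**2. What continues after withdrawal?**
- SAEs unresolved at discontinuation are followed to an outcome (Protocol 10.3.5).
- AEs are followed until resolved or clinically stable (8.5.1).
- Clinically significant abnormalities persisting at early withdrawal are followed (2.3.3).
- For potential AESIs, follow-up information and final diagnoses are submitted (8.5.6.1).
- SAEs that reach the investigator spontaneously within 6 months must be reported (8.5.1).

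**3. What stops?**
- The scheduled Month 6 SAE/AESI contact: no section provides it for a withdrawn participant.
- Twice-weekly ARI surveillance.
- In the SAP, safety phases and AESI intervals close at last contact (6.1.2, Tables 4 and 5), as does efficacy follow-up time for discontinued non-cases (6.3.3; Protocol 9.4.1.1).
- Withdrawal within 14 days of vaccination removes the participant from the PPE (Protocol 9.3). Withdrawal before Day 365 removes them from the second-year endpoints (Protocol 9.4.1.2; SAP 6.4.1.2.1).

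As an illustration, a code break on Day 15 leaves 182 − 15 = 167 days before the Day 182 contact without scheduled collection.

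**4. Size.** Inputs from the documents: N = 15,340 + 7,670 = 23,010; 2:1 allocation; placebo LRTD incidence 0.5% in later seasons; VE 65%; target of 76 events (Protocol 9.2.1, 9.5.1). Assumed: u, the share of participants unblinded by an investigator or site.

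Average incidence per later season = 1/3 × 0.5% + 2/3 × 0.5% × 0.35 = 0.1667% + 0.1167% = 0.2833%.

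LRTD events lost per later season, at most = u × 23,010 × 0.002833 = u × 65.2.

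| Assumed u | Participants | LRTD events lost per later season (at most) |
|---|---|---|
| 0.05% | 11.5 | 0.03 |
| 0.1% | 23.0 | 0.07 |
| 0.2% | 46.0 | 0.13 |
| 0.5% | 115 | 0.33 |
| 1% | 230 | 0.65 |

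Even at 1%, less than one event is lost per season. Power is not the issue.

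**5. Is the rule consistent with the rest of the plan?** If the primary analysis is negative, the study still runs until everyone has completed 6 months after vaccination (Protocol 4.1). When the study was terminated, all participants were still to be followed for safety to 6 months (SAP 6.11). Six-month safety collection therefore survives failure of the whole trial, but has no stated provision to survive one code break.

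**The case against.** The best defence is that the rule protects the endpoint. LRTD and ARI depend on participants starting an episode and rating their own symptoms on the RiiQ, and open-label reports would contaminate that. This stands for the primary analysis, but censoring the PPE at unblinding gives the same protection without ending safety collection.

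A reader might infer that safety follow-up is lost altogether for these participants, including for the suspected thrombotic event that led to the code break. The documents do not support that: the prompting event is what 10.3.5, 8.5.1, 2.3.3 and 8.5.6.1 keep following. What lacks a schedule is detection of a further, new event. Nor do the documents say that thrombotic AESIs lead to investigator unblinding. The TTS section does not call for it, and sponsor unblinding for safety reporting lets the participant stay. The link between code breaks and adverse events is a reasonable inference from the word emergency, not a stated fact.

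A reader might also infer that these participants drop out of the FAS. They do not: anyone with a documented vaccination is in it, and person-time and events to last contact count.

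It is fair to add that Section 7.2 bars further assessments only after withdrawal of consent, so a site could stay in contact, although nothing requires it. The SAP tabulates reasons for termination by group (6.2), so the number of such withdrawals could be seen, but not the missing outcomes. The loss of ARI follow-up is also less than the full 24 months unless the code is broken on Day 1, and SAP 6.11 ended ARI collection on 29 March 2023.

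**Conclusion.** The point holds in limited form. An investigator or site code break ends scheduled collection of new SAEs/AESIs to Month 6 and ARI surveillance, in a single-dose study where withdrawal serves no dosing purpose, and for a reason probably related to an adverse event. Open events are still followed and data to last contact are kept. The number affected is not given: the 12 to 46 participants at 0.05% to 0.2% are an assumption, and the true number is probably small. The effect on the primary analysis is negligible throughout the range examined. The value of a change lies in complete six-month safety data for a small, event-selected group, consistent with how the plan treats everyone else. It is a minor improvement, not a threat to the trial's conclusions.

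**What to change.** - **Protocol 7.2:** remove the code break by the investigator or site personnel from the reasons for withdrawal from the study. Keep these participants in SAE/AESI follow-up to Month 6 and in ARI follow-up for the FAS sensitivity analysis.
- **SAP 4 and 6.3.3:** add that such participants are censored in the PPE at the date of unblinding. A code break in the first 14 days would then contribute no PPE person-time, and one before Day 365 no second-year person-time, so the PPE results stay essentially as they would be now.
- **Protocol 7.2, 8.5.1 and 10.3.5:** reconcile them so that they state in one place what is collected after a code break.

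Cost: a wording change in the protocol, a short addition to the SAP (the PPE currently excludes data by study year and has no censoring at unblinding), and a little open-label, self-reported ARI data in the FAS sensitivity analysis only.
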